**\*Criteria for Hy's Law**

Hy's law is defined as drug-induced jaundice caused by hepatocellular injury, without a significant obstructive component, has a high rate of bad outcomes, from 10% to 50% mortality (or transplant). The 2 "requirements" for Hy's Law are:

- Evidence that a drug can cause hepatocellular-type injury, generally shown by an increase in transaminase elevations higher than 3x ULN (2x ULN elevations are too common in treated and untreated patients to be discriminating).
- Cases of increased bilirubin (at least 2x ULN) with concurrent transaminase elevations at least 3x ULN and no evidence of intrahepatic or extrahepatic bilirubin obstruction (elevated alkaline phosphatase) or Gilbert's syndrome.

**8.4 SAE Reporting Requirements**

Serious adverse events (SAE) are defined above. The investigator should inform PrECOG of any SAE within 24 hours of being aware of the event. The date of awareness should be noted on the report. This must be documented on the SAE form provided for this trial. This form must be completed and supplied to PrECOG within 24 hours or 1 business day at the latest on the following working day. The initial report must be as complete as possible, including details of the current illness and (serious) adverse event, and an assessment of the causal relationship between the event and the investigational product(s). Information not available at the time of the initial report (e.g., an end date for the adverse event or laboratory values received after the report) must be documented on a follow-up SAE report form. A final report to document resolution of the SAE is required. The investigator is responsible for following all SAEs until resolution, until the subject returns to baseline status, or until the condition has stabilized with the expectation that it will remain chronic, even if this extends beyond study participation. A copy of the transmission confirmation of the SAE report should be attached to the SAE and retained in the patient records.

Collection of complete information concerning SAEs is extremely important. Full descriptions of each event will be followed. Thus, follow-up information which becomes available as the SAE evolves, as well as supporting documentation (e.g., hospital discharge summaries and autopsy reports), should be collected subsequently, if not available at the time of the initial report, and immediately sent using the same procedure as the initial SAE report.

**SAEs should be scanned and emailed to [contact]** as per the instructions found in study materials provided to the investigator site.

████████████████████  
Medical Monitor  
During normal business hours:  
(8:30 am-5:00 pm EST):  
[contact]  
After normal business hours:  
Phone: ████████████████████  
████████████████████

Manager, Clinical Safety  
During normal business hours:  
(8:30 am-5:00 pm EST):  
[contact]  
After normal business hours:  
Cell: ██████████

PrECOG will have accountability for both initial and follow-up reporting of SAEs to the investigational product manufacturer and regulatory authorities within appropriate timelines.

Investigators should also report event(s) to their IRB as required.

All SAEs, regardless of causality, must be collected which occur within 30 days of last dose of study treatment. This includes all deaths within 30 days of last dose of cytarabine, daunorubicin, gilteritinib or midostaurin regardless of attribution. In addition, the Investigator should notify PrECOG or designee of any SAE that may occur after this time period which they believe to be definitely, probably or possibly related to investigational product.

**NOTE:** After study closure, study-drug related SAEs should be reported voluntarily by the treating physician directly to the manufacturer.

Serious adverse event reporting to regulatory authorities and all participating investigators will be conducted by PrECOG (or designee) in accordance with 21CFR312.32, local requirements and international regulations, as appropriate. FDA reporting requirement timelines will be followed. PrECOG will also concurrently forward any such reports to Astellas.

#### 8.5 Reporting of Other Second Primary Cancers

New cancers are those that are not the primary reason for administration of study treatment and have been identified after inclusion of the patient into the clinical study.

All cases of new primary cancers that occur during or after protocol treatment must be reported to PrECOG on a Second Primary Cancer form within 30 days of diagnosis, regardless of relationship to protocol treatment. Secondary primary malignancies should also be reported as a SAE. The SAE form is not for use for reporting recurrence or development of metastatic disease. A copy of the pathology report, if applicable, should be sent, if available.

**NOTE:** Once data regarding survival and remission status are no longer required by the protocol, no follow-up data should be submitted.

#### 8.6 Procedures in Case of Pregnancy

Prior to study enrollment, women of childbearing potential (WOCBP-not surgically sterilized and between menarche and 1 year post menopause) and male patients with a female partner of childbearing potential must be advised of the importance of avoiding pregnancy during trial participation and the potential risk factors for an unintentional pregnancy, documented in the informed consent. In addition, all WOCBP should be instructed to contact the Investigator immediately if they suspect they might be pregnant (e.g., missed or late menstrual period) at any time during study participation.

Pregnancy of a female patient or the female partner of a male patient occurring while the patient is receiving study drug or within 180 days for female patient or 120 days for female partner after the patient's last dose of study drug will be reported to PrECOG on a Pregnancy Form within 24 hours of the investigator's knowledge of the pregnancy.

All reports of congenital abnormalities/birth defects and spontaneous miscarriages should also be reported and handled as SAEs.

The outcome of all pregnancies (spontaneous miscarriage, elective termination, normal birth including health of the newborn or congenital abnormality) must be followed and documented on the Pregnancy Form even if the subject was discontinued from the study treatment. Should pregnancy occur during a subject's participation, the subject will immediately be discontinued from the treatment and followed per protocol.

The study-specific Pregnancy Form can be found in the Study Reference Manual.

8.7 Reporting Guidelines in the Case of Overdose

In the event of an overdose with any of the drugs on-study (cytarabine, daunorubicin, gilteritinib [defined as more than 300 mg for a single dose] or midostaurin), defined as any dose higher than the patient allocated dose in the study, unless otherwise noted, should be captured as an adverse event. Both symptomatic and non-symptomatic overdose must be reported. For any accidental or intentional overdose with the study treatment that is symptomatic, **even if not fulfilling a seriousness criterion**, a SAE form should also be completed and reported to PrECOG within 24 hours of the investigator's knowledge of the overdose.

## 9 Measurement of Effect

Response assessments will require a bone marrow aspirate/biopsy to be performed. The 2017 European LeukemiaNet (ELN) recommendations will be used to assess response.

End of Cycle = Count Recovery

A bone marrow aspirate/biopsy is required on all patients on Day 21 (+/- 1 day window; delays due to holidays, weekends, or other unforeseen circumstances will be permitted) after initiating the first cycle of induction. Patients who have residual disease will be eligible to receive a second cycle of induction identical to the first (Section 10).

A repeat bone marrow aspirate/biopsy should be done to assess for response and MRD upon count recovery (Absolute Neutrophil Count (ANC)  $\geq$  1000/mm^3, platelets  $\geq$  100,000/mm^3) but no later than Day 60 after initiation of the cycle of induction therapy (i.e., Day 60 or patients who receive one cycle of induction and Day 84-105 for patients that receive 2 cycles of induction. (MRD sample will be obtained by Day 60 on all patients even if counts have not recovered. The only exception is a patient who has been declared a relapse based on blood counts).

Patients who do not achieve a CR or CRi by Day 60 after initiation of the last cycle of induction therapy will be removed from study.

Patients are not eligible to proceed to Consolidation unless bone marrow samples are obtained for MRD at the time of CR/CRi.

A bone marrow aspirate/biopsy is also required at the end of the first Consolidation cycle to assess disease and MRD status.

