#### **ARM B (7+3) + Midostaurin**

- **Cytarabine** 100 mg/m^2/day will be administered by continuous IV infusion for a total of 7 days beginning Day 1
- **Daunorubicin** 90 mg/m^2/day will be administered IV per package insert or per institutional guidelines or over 30-60 minutes Days 1,2,3.
- **Midostaurin** 50 mg orally BID x 14 days beginning on day 8

If there is a delay in starting FLT3 inhibitors in Arm A or Arm B (due to obtaining drug, i.e. insurance, formulary, etc.), the FLT3 inhibitor will need to stop after Day 21 dose (i.e., Day 21 or Day 22 [if FLT3 inhibitor started on Day 9]). No missed doses will be made up.

**NOTE:** If second cycle of induction is needed, daunorubicin dose will be decreased to 45 mg/m^2/day IV Days 1,2,3.

---

A bone marrow aspirate/biopsy will be performed on all patients on Day 21 (+/-1 day window; delays due to holidays, weekends, or other unforeseen circumstances will be permitted) to determine the need for a second induction cycle. If the marrow aspirate/biopsy is inadequate to make a determination, consider repeating the bone marrow assessment in 5-7 days.

**Arm A + Gilteritinib:** If second cycle of induction is planned, treatment will begin after Day 28 (i.e.,  $\geq 7$  days after completing gilteritinib) but no later than Day 45.

**Arm B + Midostaurin:** If second cycle of induction is planned, treatment will begin after Day 24 (i.e.,  $\geq 3$  days after completing midostaurin) but no later than Day 45.

A repeat bone marrow aspirate/biopsy should be done to assess for response and MRD status upon peripheral blood count recovery (Absolute Neutrophil Count (ANC)  $\geq 1000/\text{mm}^3$ , platelets  $\geq 100,000/\text{mm}^3$ ) but no later than Day 60 after initiation of the first cycle of induction therapy for patients who receive 1 cycle of induction or no later than Day 60 after initiation of the second cycle of induction therapy (i.e., Day 84-105) for patients who receive 2 cycles of induction (MRD sample will be obtained by Day 60 on all patients even if counts have not recovered. The only exception is a patient who has been declared a relapse based on blood counts).

Patients who do not achieve a CR or CR with incomplete hematologic recovery (CRi) by Day 60 if one cycle and Day 84-105 if 2 cycles of induction therapy will be removed from study.

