**Arm A (7+3 + Gilteritinib)**

- **Cytarabine** 100 mg/m^2/day will be administered by continuous IV infusion for a total of 7 days beginning Day 1
- **Daunorubicin** 90 mg/m^2/day will be administered IV per package insert or institutional guidelines or over 30-60 minutes Days 1,2,3 (45 mg/m^2/day if receives second cycle of induction)
- **Gilteritinib** 120 mg orally QD x 14 days starting on day 8

If second cycle of induction is needed, treatment will begin after Day 28 (i.e.,  $\geq 7$  days after completing gilteritinib) but no later than Day 45.

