#### **5.2. Bone Marrow Aspirate/Biopsy**

A bone marrow aspirate/biopsy is required on all patients on Day 21 after initiating the first cycle of induction. Patients who have residual disease will be eligible to receive a second cycle of induction.

A repeat bone marrow aspirate/biopsy should be done to assess for response and MRD upon count recovery (Absolute Neutrophil Count (ANC)  $\geq 1000/\text{mm}^3$ , platelets  $\geq 100,000/\text{mm}^3$ ) but no later than Day 60 after initiation of the cycle of induction therapy (i.e., Day 60 or patients who receive one cycle of induction and Day 84-105 for patients that receive 2 cycles of induction).

Patients who do not achieve a CR or CRi by Day 60 after initiation of the last cycle of induction therapy will be removed from study.

Patients are not eligible to proceed to Consolidation unless bone marrow samples are obtained for MRD at the time of CR/CRi.

A bone marrow aspirate/biopsy is also required at end of Consolidation to assess disease status.

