### Arm A (7+3 + Gilteritinib)

- Cytarabine 100 mg/m^2/day will be administered by continuous IV infusion for a total of 7 days beginning Day 1
- Daunorubicin 90 mg/m^2/day will be administered IV per package insert or institutional guidelines or over 30-60 minutes Days 1,2,3 (45 mg/m^2/day if receives second cycle of induction)
- Gilteritinib 120 mg orally QD x 14 days starting on day 8

If second cycle of induction is needed, treatment will begin after Day 28 (i.e., ≥ 7 days after completing gilteritinib) but no later than Day 45.

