### ARM B (7+3) + Midostaurin

- Cytarabine 100 mg/m^2/day will be administered by continuous IV infusion for a total of 7 days beginning Day 1
- Daunorubicin 90 mg/m^2/day will be administered IV per package insert or institutional guidelines or over 30-60 minutes Days 1,2,3 (45 mg/m^2/day if receives second cycle of induction)
- Midostaurin 50 mg orally BID x 14 days beginning on day 8

If second cycle of induction is needed, treatment will begin after Day 24 (i.e., ≥ 3 days after completing midostaurin) but no later than Day 45.

If there is a delay in starting FLT3 inhibitors in Arm A or Arm B (due to obtaining drug, i.e. insurance, formulary, etc.), the FLT3 inhibitor will need to stop after Day 21 dose (i.e., Day 21 or Day 22 [if FLT3 inhibitor started on Day 9]). No missed doses will be made up.

See Section 5 for dosing instructions and additional information for gilteritinib and midostaurin administration and Section 6 for dose delays/modifications. If CR or CRi is not achieved, a second induction cycle of therapy may be administered.

**NOTE:** Patients are not eligible to proceed to consolidation unless bone marrow samples are obtained for MRD at time oCR/CRi.

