#### Study Schema

Accrual Goal: 179

- 1 Any patient undergoing bone marrow biopsy with suspicion of or known diagnosis of AML will be asked to sign a Prescreening Consent in order to confirm diagnosis and determination/confirmation of FLT3 status at central laboratory and obtain research samples for the study prior to randomization.
- 2 Daunorubicin 90 mg/m^2/day will be administered IV over 30-60 minutes Days 1,2,3 (45 mg/m^2/day if receives second cycle of induction).
- 3 Patients may proceed to allogeneic TRANSPLANT after induction or after 0-4 cycles of consolidation.
- 4 Patients will go off treatment at the time of transplant or any non-protocol leukemia directed therapy.
- 5 If Complete Response (CR) or CR with incomplete hematologic recovery (CRI) is not achieved, a second induction cycle of therapy may be administered.
- 6 For patients age  $\geq 55$  reduce consolidation cytarabine dose to 1.5 g/m^2.

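### After pancreatitis, Table 6-3 restarts gilteritinib at a fixed 80 mg, which conflicts with the re-escalation bar for a patient already at 40 mg; the second-induction and PRES wording also need reconciling (minor)

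*Protocol*

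**What the plan says.** **Gilteritinib after pancreatitis (main item).** Table 6-2 sets three dose levels: 120, 80 and 40 mg. Section 6.1.2 allows at most two reductions, taken step by step. It rules out re-escalation after a reduction unless there was a specific cause, not related to gilteritinib, for the hold or reduction. The pancreatitis row of Table 6-3 interrupts dosing until resolution and then resumes at 80 mg, without mention of the dose in use before the event. The three general rows of the table (first, second and third occurrence of a related Grade 3 or higher non-hematological event) each exclude pancreatitis and refer the reader to its own row.

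**Second induction.** Protocol Section 9 says "Patients who have residual disease will be eligible to receive a second cycle of induction identical to the first (Section 10". The Section 5.2.1 note says "If second cycle of induction is needed, daunorubicin dose will be decreased to 45" mg/m2/day. Section 10, footnote 21, gives the cycle-2 dose in the same line as the first: "over 30-60 minutes Days 1,2,3 (45 mg/m"2/day for a second cycle. The Study Schema and Section 11.3.4 agree with footnote 21. So does the SAP, in Appendix I for Arm A ("per package insert or institutional guidelines or over 30-60 minutes Days 1,2,3 (45 mg/m"2) and Arm B ("day if receives second cycle of induction"), and in the Appendix II schema ("will be administered IV over 30-60 minutes Days 1,2,3 (45 mg/m"2). SAP Section 5.2 carries the Section 9 sentence in a shorter form: "Patients who have residual disease will be eligible to receive a second cycle of induction".

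**PRES.** Table 6-3 tells the site to contact the sponsor and stop gilteritinib. Section 11.1.9.1 says that stopping should be considered. It also describes two cases from an earlier study, in one of which the patient stayed on the drug.

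**The concern.** These are treatment instructions that sites act on. Where two passages point in different directions, two sites can treat the same situation differently and each cite the protocol. The same action can then be classed as compliant under one section and as a deviation under another. The 40 mg pancreatitis case is the most serious of the three, because literal compliance with the table breaches a rule stated just before it. What is at stake is patient safety and consistent classification of deviations. The trial's inference is not at stake.

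**Working it through.** The documents state no figure to reproduce. The check sets the passages side by side and does simple arithmetic on the stated doses.

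**1. Pancreatitis row against Section 6.1.2.** Change on restart = (80 − dose before the event) / dose before the event.

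| Dose before the event | Change on restart at 80 mg | Against Section 6.1.2 |
|---|---|---|
| 120 mg | (80 − 120)/120 = −33% | one level down; no conflict |
| 80 mg | (80 − 80)/80 = 0% | no reduction; may be an intended carve-out |
| 40 mg | (80 − 40)/40 = +100% | one level up; meets the re-escalation bar |

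Can a patient reach 40 mg? Yes, within the table itself. The first- and second-occurrence rows each restart at a reduced dose (120 to 80, then 80 to 40 mg) and apply only to events judged related to the drug. Two confirmed QTcF >500 ms events lead to the same place. Pancreatitis would then restart the patient at 80 mg.

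Does another rule resolve the case?
- The third-occurrence row, which stops the drug, excludes pancreatitis.
- The exception to the re-escalation bar concerns causes other than gilteritinib. The pancreatitis row is not limited to such events, and Section 11.1.10.3 lists pancreatitis among the drug's potential risks.
- If the pancreatitis itself is judged unrelated, Section 6.1.2 lets the original dose resume. For this patient that is 40 mg, so the row's 80 mg still does not follow.

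The QTcF >500 ms row of the same table does depend on current dose, distinguishing a patient already at 80 mg. The pancreatitis row does not.

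**2. Second induction.** The daunorubicin inputs are 90 mg/m2/day in cycle 1 (Section 5.2.1) and 45 mg/m2/day in cycle 2 (Sections 5.2.1, 10 and 11.3.4), each on three days.
- Cycle 1: 3 × 90 = 270 mg/m2.
- Cycle 2 as stated in those sections: 3 × 45 = 135 mg/m2.
- Cycle 2 if identical to cycle 1: 270 mg/m2.
- Two-cycle totals: 270 + 135 = 405 against 270 + 270 = 540 mg/m2; 540/405 − 1 = 33%.

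The cycle-2 dose is stated in five protocol places (Study Schema, Section 5.2.1, footnote 21 for each arm, Section 11.3.4) and three SAP places (Appendix I for each arm, Appendix II). The two cycles cannot be identical if those eight statements hold.

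**3. PRES.** Stopping gilteritinib satisfies both passages. Continuing after consideration satisfies Section 11.1.9.1 and breaches Table 6-3. The difference is one of strength, and it matters only when a site continues.

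**The case against.** The case against giving this much weight is good in several respects.

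- **Discretion exists.** Table 6-3 is headed as guidelines. Section 6.1.2 lets the investigator interrupt or reduce dosing for subject safety for reasons outside the table, with prompt notice to the sponsor. That gives a documented route for an unforeseen case and lowers the practical risk. It does not remove the conflict, because the row still names a dose that the re-escalation bar forbids.
- **The 40 mg case is narrow.** It needs two earlier reductions and then pancreatitis in one patient. This stands.
- **The second-induction phrase is easily resolved by a reader.** Section 9 concerns response assessment, states no dose, and points to Section 10, which gives one. A reader might infer that the protocol directs a full-dose second cycle and 540 mg/m2 overall. The documents do not support that: a site would have to ignore the pointer in the sentence and the treatment section.
- **PRES is not a strict contradiction,** since one course of action meets both texts. Section 5.2.3 also refers discontinuation criteria to Section 6 and/or 7.3, and the table requires contact with the sponsor. What stands is that the two sections are worded differently on whether continuing is open to the site.

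A reader might also extend the point to overdose reporting. For daunorubicin, Section 8.7 has an overdose "defined as any dose higher than the patient allocated dose in the study, unless otherwise noted, should be captured as an adverse event", so a single description of the allocated cycle-2 dose is desirable. For gilteritinib the same section sets its own threshold of more than 300 mg in a single dose. A restart at 80 mg is therefore not a reportable overdose.

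**Conclusion.** The inconsistency is real and minor. Only the 40 mg pancreatitis case is one in which both instructions cannot be met: a 100% increase against a rule that bars increases. That conclusion assumes the earlier reductions were for gilteritinib-related reasons; otherwise the exception in Section 6.1.2 could apply. The second-induction and PRES items are wording differences of lesser weight.

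Two neighbouring readings go further than the text. Restart at 80 mg for a patient already at 80 mg may be intended, given the explicit exclusion of pancreatitis from the general rows. The QTcF >500 ms row says nothing about a patient at 40 mg, which is silence and not contradiction.

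The documents give no rate for second inductions, pancreatitis or reductions to 40 mg, so the number of patients affected cannot be estimated. The two PRES cases come from a relapsed/refractory study and give no rate for this population. Nothing here bears on the primary endpoint, alpha, power or sample size.

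**What to change.** Issue a clarification letter, or use the next amendment, to reconcile:

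1. the pancreatitis row of Table 6-3 with Section 6.1.2, for patients whose dose has already been reduced;
2. the second-induction sentence in Section 9 with Sections 5.2.1, 10 and 11.3.4;
3. Section 11.1.9.1 with the PRES row of Table 6-3.

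One instruction should stand in each case. The sponsor's clinical team decides which; no dose or rule is proposed here. The SAP appendices reproduce dosing text, so they should be checked against the reconciled protocol.

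The cost is a few lines of wording, with no change to any analysis. Section 12.3.1 records the interim futility analysis, planned at 90 patients with MRD data, as complete, so part of the induction treatment predates any correction. For those patients the reconciled text would still help to classify deviations consistently.
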